EFFICACY EVALUATIONS	
 Sensation of stimulation experienced by the patient Number of days taken to wean

	
 • Time spent breathing without mechanical ventilation support • Respiratory muscle strength • Peak expiratory flow • Resting breathing parameters
PRIMARY ENDPOINT	
 • Maximum inspiratory and expiratory pressure
SECONDARY ENDPOINTS	
 • Thickness of the abdominal wall muscles • Thickness of the diaphragm • Weaning success • Number of days taken to wean • Time spent breathing without mechanical ventilation support • Cough peak flow • Resting breathing parameters • Adherence to the study protocol • Sensation of stimulation experienced by the patient • Adverse events
STATISTICS Analysis Plan	
Only participants who fulfil the protocol in terms of eligibility, interventions and outcome assessment will be included in the statistical analysis.
 
Study results will first undergo descriptive level statistical analyses. In the second level of analysis, we will quantify the magnitude to which abdominal NMES exhibits a protective effect using regression models.
 
Weaning success will be compared between the study groups using Poisson regression. Kaplan Meier survival analysis will be used to compare the time to wean in both study groups.
 
Adverse event rates will be coded by body system and MedDra classification term. Adverse events will be tabulated by treatment group and will include the number of patients for whom the event occurred, the rate of occurrence, and the severity and relationship to study treatment.

Rationale for Number of Participants	
This study is intended to be a pilot study that will be used to obtain initial data on the feasibility and safety of VentFree to assist in the process of ventilator weaning. The primary outcome of this study is the effect of abdominal NMES on respiratory muscle strength over time. There is currently no data in the literature to support a sample size calculation for this study. Given this constraint, in this pilot study a total of 24 participants was deemed adequate and is consistent with sample size recommendations in the literature.¹ Allowing for a 10% drop out rate, a total of 26 participants will be recruited for this study. The data collected on the secondary endpoints will be used to

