3.3 Current Standard of Care

A recent international symposium generated guidelines for weaning from MV. These guidelines state that active weaning from MV should commence when the pathology responsible for the institution of MV has been resolved and when the patients are clinically stable.¹³ A weaning trial commonly consists of a period of completely unsupported breathing (e.g., T-tube trial) or a period of minimal ventilator support (e.g., pressure support ventilation). If the patient does well during the weaning trial (i.e. is able to comfortably breathe unassisted) he/she is extubated; otherwise, the patient resumes MV.¹³

When patients do not pass the first weaning trial, the potential mechanisms for weaning failure must be identified and addressed.¹³ In addition, the aforementioned guidelines suggest implementing daily SBTs, during which the work of breathing accomplished by the ventilator is progressively reduced, and thus, the respiratory muscles weakened during the preceding pre-weaning period of MV are reconditioned.^{9,15}

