7.2 Secondary Outcome Measures

The secondary outcome measures in this study are:

- **Thickness of the Abdominal Wall Muscles** – The end inspiratory and end expiratory thickness of the external oblique, internal oblique and transversus abdominis muscles will be measured using ultrasound.
- **Thickness of the Diaphragm** - The end inspiratory and end expiratory thickness of the diaphragm will be measured using ultrasound.
- **Weaning Success** – Defined as 72 hours of spontaneous respiration without any mechanical ventilation support.
- **Number of Days Taken to Wean** – Defined as the time from the patient's original admission to the point of weaning success.
- **Time spent breathing without mechanical ventilation support** - The time spent breathing without MV support will be recorded on a daily basis throughout the study.
- **Cough Peak Flow** – The peak flow during a voluntary cough will be recorded.
- **Resting Breathing** – This outcome will be assessed using measurements of tidal volume, respiratory rate and minute ventilation during a one-minute period of resting breathing.
- **Adherence to the Weaning Protocol** – The number and duration of the weaning sessions supported by electrical stimulation during the study period will be recorded for each participant.
- **Sensation of Stimulation Experienced by the Patient** – Surface electrical muscle stimulation stimulates sensory nerves in addition to motor nerves and can cause pain at high intensities. The degree of discomfort experienced by participants during stimulation will be quantified using the behavioral pain scale.¹⁸
- **Adverse Events** – All medical complications experienced by the study participants during the study will be assessed for severity and relationship to the study device and recorded.

8 Participant Selection

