In the second level of analysis, we will quantify the magnitude to which abdominal NMES exhibits a protective effect. Crude and adjusted linear regression models will be carried out where the outcome variable is continuous and the covariates are normally distributed or categorical. Our prior experience with measures of respiratory function, which will be measured in this study, indicate that select covariates may need to be controlled for or otherwise do not always fit a normal distribution. Therefore, crude and adjusted generalized linear models are anticipated. These regression models will be carried out at the point of successful wean. All multiple regression covariates, linear or generalized, will be assessed for interaction, collinearity and confounding. For all unadjusted and adjusted multinomial models the overall model log likelihood ratio and Hosmer and Lameshow goodness-of-fit will be conducted to ensure models report significance and are not over fitted. Adjusted regression models will undergo sensitivity analysis and bootstrap analyses. Bootstrap analysis is a re-sampling strategy to estimate the population parameter of interest based on the observed, sample data.

The number of tries to successful wean will be quantified using Poisson regression. Crude and adjusted models will be carried out. Kaplan-Meier survival analysis will be carried out to quantify differences in the time to wean in the treatment abdominal NMES modality compared to the control. As the patients will be resident in hospital facilities, we do not anticipate significant methodological concerns with respect to censoring.

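### Poisson regression is assigned to yes/no weaning success in the synopsis and to an uncollected count of weaning attempts in Section 17, with no variance method stated for the crude model

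*Combined protocol and SAP*

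**What the plan says.** The synopsis (Section 2, Statistics Analysis Plan) states: "Weaning success will be compared between the study groups using Poisson regression". Section 17 gives the same method a different outcome: "The number of tries to successful wean will be quantified using Poisson regression". It adds only that crude and adjusted versions will be fitted.

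Section 7.2 fixes weaning success as a threshold: "Defined as 72 hours of spontaneous respiration without any mechanical ventilation support". Each participant either reaches it or does not.

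Elsewhere Section 17 refers to other models in general terms: "Therefore, crude and adjusted generalized linear models are anticipated", and "For all unadjusted and adjusted multinomial models the overall model log likelihood ratio" is to be examined together with a goodness-of-fit test. Neither statement is linked to weaning success. Categorical variables are to be summarised as proportions and counts, and Kaplan-Meier is reserved for time to wean. The nearest text to a variance method is: "Adjusted regression models will undergo sensitivity analysis and bootstrap analyses". Section 17 describes the bootstrap as a way to estimate a parameter and does not mention standard errors or intervals.

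**The concern.** One method has two different outcomes, and each pairing has a problem.

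Paired with weaning success, Poisson regression gives a valid risk ratio. Its default variance, however, assumes that the variance equals the mean. A yes/no outcome has variance p(1-p), which is smaller than its mean p, so the default interval is too wide and the Wald test rejects too rarely. Sandwich variance corrects this, but the plan does not ask for it. The same data under the same named method can then include or exclude no effect, depending on a software setting that the plan leaves open.

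Paired with the number of tries, the model has no defined outcome. Section 3.3 describes weaning trials only in general ("A weaning trial commonly consists of a period of completely unsupported breathing"), and nothing says what counts as one try. The daily record does not supply it: "The time spent breathing without MV support will be recorded on a daily basis throughout the study" gives a duration, not a number of attempts. The adherence outcome in Section 7.2 counts sessions supported by stimulation. A count up to successful weaning also does not exist for participants who never wean, so they would drop out of the comparison.

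At stake are the interval and test for a weaning endpoint. Section 17.1 says that data on the secondary endpoints will be used to size a later trial on weaning outcome.

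**Working it through.** **Inputs from the documents.** The target is 24 participants (Section 17.1), with 1:1 allocation (Section 9.1), so 12 per arm (Section 6). The recruitment figure of 26 can be reproduced to within rounding: 24 × 1.1 = 26.4 and 24/0.9 = 26.7. At 10% dropout, 26 × 0.9 = 23.4, so about 12 per arm is the right size for the check.

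**Assumptions.** The documents give no weaning rates, significance level or named test for this endpoint. I assume a two-sided 5% level and show a range of rates.

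**Standard error of the log risk ratio.** With a and b participants weaned out of n = 12 per arm:
- model-based Poisson: sqrt(1/a + 1/b)
- robust (sandwich): sqrt(1/a + 1/b − 2/n)

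At a common rate p the ratio of the two is 1/sqrt(1−p):
- p = 0.2: 1/sqrt(0.8) = 1.12
- p = 0.5: 1/sqrt(0.5) = 1.41

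**Type I error and power.** These come from exact enumeration of all 13 × 13 possible tables. The Wald and robust tests count a table with an empty arm as no rejection. The likelihood-ratio statistic is 2[a ln(2a/(a+b)) + b ln(2b/(a+b))], compared with 3.84.

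| Weaning rates | Model-based Wald | Likelihood ratio | Robust | Fisher |
|---|---|---|---|---|
| 20% both | 0.02% | 6.9% | 0.2% | 1.2% |
| 30% both | 0.14% | 4.1% | 1.0% | 1.7% |
| 40% both | 0.24% | 2.4% | 1.9% | 2.1% |
| 50% both | 0.21% | 1.2% | 2.4% | 2.3% |
| 60% both | 0.12% | 0.5% | 2.8% | 2.1% |
| 10% vs 50% | 8% | 55% | 20% | 42% |
| 20% vs 60% | 12% | 39% | 33% | 39% |
| 30% vs 70% | 11% | 27% | 38% | 39% |
| 40% vs 80% | 9% | 17% | 43% | 39% |

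An arm with no events, which leaves no risk ratio, occurs with probability 28% at 10% vs 50% and 7% at 20% vs 60%.

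**Illustration: 10/12 vs 4/12 weaned.** The risk ratio is 2.50, with log 0.916.
- Model-based: SE = sqrt(0.10 + 0.25) = 0.592, 95% CI 0.78 to 7.97, p = 0.121.
- Robust: SE = sqrt(0.35 − 0.167) = 0.428, 95% CI 1.08 to 5.79, p = 0.032.
- Risk difference: 50 points, Newcombe 95% CI 11 to 73, Fisher p = 0.036.

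**The proposed replacement.** Newcombe 95% coverage at equal rates of 20%, 30%, 40%, 50% and 60% is 96.1%, 95.1%, 94.1%, 93.6% and 94.1%. Read as a test, the interval would therefore reject 5.9%, 6.4% and 5.9% of the time at 40%, 50% and 60%. It can also disagree with Fisher: 9/12 vs 4/12 gives 2 to 67 points but Fisher p = 0.100.

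**The case against.** Four points can fairly be made for the plan.

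*The synopsis does name a comparison of weaning success.* This stands. A reader might infer that the trial has no plan at all for the proportion weaned. The gap is in Section 17 only, which diverges from the synopsis instead of carrying its comparison through.

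*The bootstrap may reach the adjusted Poisson model.* This stands in part. Section 17 applies it to adjusted regression models without excluding Poisson. It does not reach the crude model, and no sentence ties it to standard errors.

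*Robust Poisson would be enough.* At middle and higher rates it largely is: 43% power against 39% for Fisher at 40% vs 80%, and type I error no higher than 2.8% in the table. It would also keep the planned crude and adjusted models. It is clearly weaker at low rates (20% against 42% power at 10% vs 50%) and gives no estimate when an arm is empty. That supports keeping it in a supportive role.

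*This is a secondary endpoint in a pilot.* True, and it limits the weight of the point.

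A reader might also infer that participants off support for less than 72 hours at their last visit cannot be classified. The Section 7.2 definition answers that: they have not met it and count as not weaned. Nor do the figures show a general excess of false positives. The model-based Wald test errs towards not rejecting, and the only inflation seen for Poisson is the likelihood-ratio test at 20% (6.9%).

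**Conclusion.** The point holds. Two sections give one method two different outcomes. One of them is undefined, uncollected and missing by construction for participants who never wean. The other is yes/no, and the crude model has no stated variance method.

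The size depends on the assumed rates, the assumed 5% level and use of default model-based variance. On those terms, the standard error is 12% to 41% too large at weaning rates of 20% to 50%, and the Wald test has almost no chance of rejecting at 12 per arm. The risk ratio estimate and the observed proportions do not change, and the primary endpoint is not touched. The change is worth making before analysis because it is cheap and takes the choice of variance out of the analyst's hands.

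**What to change.** Make the synopsis and Section 17 both name weaning success as defined in Section 7.2, and delete the model for number of tries. Suggested text: *The proportion of participants with weaning success (Section 7.2) will be compared between groups as a difference in proportions with a Newcombe score-based 95% confidence interval. This is the main result and is intended for estimation. If a p-value is reported, it will come from Fisher's exact test, and any statement of significance will rest on that test alone.*

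If crude and adjusted risk ratios are kept, specify Poisson regression with robust (sandwich) variance as supportive. State that it gives no estimate when an arm has no events and is conservative at low rates.

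The cost is a few sentences in two places and no new data. There are three downsides: the main comparison is unadjusted, Fisher's test is conservative (1.2% to 2.3% at equal rates of 20% to 60%), and Newcombe coverage dips slightly below nominal at middle rates (93.6% at 50%).

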12.6 Early Withdrawal Visit

In the case that the patient withdraws or is withdrawn from the protocol (see Section 14) before the end of the intervention period, and providing the patient consents, then the investigators will perform and record the participant's MEP, MIP, thickness of the abdominal wall muscles and diaphragm, CPF, resting breathing parameters and adverse events related to stimulation or otherwise.

If the participant is withdrawn from the study because they have successfully weaned from mechanical ventilation then the study researcher will also calculate and record the number of days taken to wean taken from the institution of mechanical ventilation.

13 Adverse Experience Reporting and Documentation

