14.1 Withdrawal of Participants from the Study

A participant may be withdrawn from study treatment at any time if the participant, the investigator, or the Sponsor feels that it is not in the participant's best interest to continue. The following is a list of possible reasons for study treatment discontinuation:

- Successful weaning from mechanical ventilation
- Participant withdrawal of consent
- Participant is not compliant with study procedures
- Adverse event that in the opinion of the investigator would be in the best interest of the participant to discontinue study treatment
- Protocol violation requiring discontinuation of study treatment
- Lost to follow-up
- Sponsor request for early termination of study
- Positive pregnancy test (females)

If a participant is withdrawn from treatment due to an adverse event, the participant will be followed and treated by the PI until the abnormal parameter or symptom has resolved or stabilized.

All participants who discontinue study treatment should come in for an early discontinuation visit as soon as possible.

All participants are free to withdraw from participation at any time, for any reason, specified or unspecified, and without prejudice. This will not affect the care they receive, now or in the future.

Reasonable attempts will be made by the investigator to provide a reason for participant withdrawals. The reason for the participant's withdrawal from the study will be specified in the participant's source documents.

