12.3 Replacement of Participants

While it is estimated that 24 is a suitable sample size for this study, the actual study sample size of 26 allows for a 10% drop out rate. Therefore, up to two participants who withdraw from the study will be replaced.

15 Protocol Violations

A protocol violation occurs when the participant, investigator, or Sponsor fails to adhere to significant protocol requirements affecting the inclusion, exclusion, participant safety and primary endpoint criteria.

Failure to comply with Good Clinical Practice (GCP) guidelines will also result in a protocol violation. The Sponsor will determine if a protocol violation will result in withdrawal of a participant.

When a protocol violation occurs, it will be discussed with the investigator and a Protocol Violation Form detailing the violation will be generated. This form will be signed by a Sponsor representative and the Investigator. A copy of the form will be filed in the site's regulatory binder and in the Sponsor's files.

16 Protocol Amendments

Amendments to the clinical investigation plan must be submitted to the Sponsor for review before submitting to the appropriate IRB for approval.

17 Statistical Methods and Considerations

Only participants who fulfil the protocol in terms of eligibility, interventions and outcome assessment will be included in the statistical analysis. Patient variables will be presented using means and standard deviations for continuous normally distributed variables, medians and interquartile ranges for continuous non-normally distributed variables, and proportions and absolute numbers for categorical variables.

Adverse event rates will be coded by body system and MedDra classification term. Adverse events will be tabulated by treatment group and will include the number of patients for whom the event occurred, the rate of occurrence, and the severity and relationship to study treatment.

Study results will first undergo descriptive level statistical analyses. For continuous variables, Two-way, Student's t-tests will then be carried out using unequal variances where the variables are normally distributed. Tests for normality will be carried out using the Shapiro-Wilk method. Variables that are not normal in distribution that also cannot be log transformed to a normal distribution curve will be analysed using the Mann-Whitney U test or other non-parametric methods to be determined based on actual data distributions.

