22 APPENDIX A: SCHEDULE OF EVENTS

	Baseline Day 1	Stimulation Visits Days 2 - 22	Intermediate Visit Day 23	Stimulation Visits Days 24 - 44	Final Visit Day 45	Early Withdrawal
Informed Consent	X					
Randomization	X					
Medical History	X					
Concomitant Medications	X		X		X	X
Complete Physical Exam	X					
Height	X					
Weight	X					
Vital Signs	X					
Oximetry	X					
Expiratory Flow Limitation	X					
APACHE II	X					
Maximum Expiratory Pressure	X		X		X	X
Maximum Inspiratory Pressure	X		X		X	X
Abdominal Wall Thickness	X		X		X	
Diaphragm Thickness	X		X		X	
Cough Peak Flow	X		X		X	X
Tidal Volume	X		X		X	X
Respiratory Rate	X		X		X	X
Minute Ventilation	X		X		X	X
Administration of Stimulation		X		X		
Sensation of Stimulation		X		X		
Adverse Events	X	X	X	X	X	X
Time spent breathing without mechanical ventilation support	X	X	X	X	X	X
Number of Days Taken to Wean						X

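### Weaning status is not scheduled after a participant stops stimulation unweaned, so excluding or censoring these participants may bias the weaning results

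*Combined protocol and SAP*

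**What the plan says.** **Analysis.** Section 17 states: "Kaplan-Meier survival analysis will be carried out to quantify differences in the time to wean in the treatment abdominal NMES modality compared to the control". It gives no censoring rule, no rule for death and no sensitivity analysis for early stoppers. On censoring it says only: "As the patients will be resident in hospital facilities, we do not anticipate significant methodological concerns with respect to censoring". The same section, like the synopsis, restricts the analysis set: "Only participants who fulfil the protocol in terms of eligibility, interventions and outcome assessment will be included in the statistical analysis". The synopsis adds that weaning success will be compared by Poisson regression.

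**Stopping.** Section 14.1 lists reasons for ending study treatment. Besides weaning they include adverse event, non-compliance, protocol violation and loss to follow-up, and the investigator or sponsor may also withdraw someone in the participant's interest. Section 15 adds: "The Sponsor will determine if a protocol violation will result in withdrawal of a participant".

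**Data after stopping.** Section 14.1 asks for one visit: "All participants who discontinue study treatment should come in for an early discontinuation visit as soon as possible". Section 12.6 describes it, with the trigger "In the case that the patient withdraws or is withdrawn from the protocol (see Section 14) before the end of the intervention period". Days to wean are recorded there under one condition: "If the participant is withdrawn from the study because they have successfully weaned from mechanical ventilation". In Appendix A the row "Number of Days Taken to Wean" has a single mark, in the Early Withdrawal column, and no column follows. The only later follow-up described is of an adverse event until it resolves or stabilises (Section 14.1). Section 7.2 records ventilator-free time daily for the length of the study but does not say that this continues after withdrawal.

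**The concern.** Someone who stops on, say, Day 10 while still ventilated has no scheduled weaning status from then to Day 45. If that person is censored, Kaplan-Meier assumes that their later chance of weaning equals that of participants still under observation. If they are excluded, the comparison is between those who remain, not between the randomised groups.

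Some stopping reasons could plausibly be related to weaning prospects, adverse events above all. The arms also differ in ways that could make stopping unequal. Active current is 90% of the tolerated maximum and placebo is fixed at 10 mA (Sections 9.3.1 and 9.3.2). Personnel who apply stimulation know the allocation (Section 9.2).

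Weaning outcome is a secondary objective (Section 5), and Section 17.1 says the secondary-endpoint data will be used to size a future trial on weaning. With about 12 per arm, two or three unknown outcomes matter.

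**Working it through.** **The plan's own figure.** Section 17.1 takes 24 participants, allows 10% drop-out and recruits up to 26. 24/0.9 = 26.7 and 24 × 1.10 = 26.4, so 26 agrees to within rounding. Expected drop-outs: 26 × 0.10 = 2.6, that is 2 to 3 people. No power, alpha or event count is given for time to wean, so there is nothing further to reproduce.

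**Assumptions.** The documents give no weaning rate and no stopping rate by arm. Below, p is the true proportion weaned by Day 45 and f is the share of the *whole arm* that stops early.

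**One arm of 13, p = 50% (6.5 expected weaners), k stoppers leaving before any weaning event**

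- All stoppers would never wean: estimate = 6.5/(13 − k). For k = 2, 6.5/11 = 59%; for k = 3, 6.5/10 = 65%.
- All stoppers would have weaned: estimate = (6.5 − k)/(13 − k). For k = 2, 4.5/11 = 41%; for k = 3, 3.5/10 = 35%.

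The error can go either way.

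**Between arms, no true effect, p = 50%, stoppers excluded.** If only non-weaners stop, the expected proportion weaned is about 0.5/(1 − f).

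| Stopping, active v placebo | Active | Placebo | Difference if excluded | Difference if censored (simulated) |
|---|---|---|---|---|
| 10% v 10% | 0.5/0.90 = 55.6% | 55.6% | 0 | about 0 |
| 15% v 5% | 0.5/0.85 = 58.8% | 0.5/0.95 = 52.6% | +6 points | about +5 points |
| 20% v 0% | 0.5/0.80 = 62.5% | 50.0% | +12.5 points | about +11 points |

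The censored column comes from 1,500 simulated trials per setting: 13 per arm, constant weaning hazard, stopping spread evenly over the first half of follow-up. The one-directional log-rank false-positive rate, nominally 2.5%, was about 5% at 15% v 5% by either route. At 20% v 0% it was about 8% if censored and 10% if excluded.

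**Partly linked stopping.** Let half the stoppers be non-weaners only and half be random, so that weaners lose 0.5 × f × 0.5 of the arm. At 15% v 5% under exclusion: (0.5 − 0.0375)/0.85 = 54.4% v (0.5 − 0.0125)/0.95 = 51.3%, or about +3 points. A simulation with censoring also gave about +3.

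**Unrelated stopping.** The difference was about zero in every setting, whether stopping was equal or unequal.

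**How strong the assumptions are.** In both unequal rows the pooled stopping rate is 10%, which matches the plan's allowance. With p = 50%, however, 15% of an arm is 0.15/0.5 = 30% of its non-weaners, and 20% is 40%. If 15% v 5% is read instead as a share of non-weaners, exclusion gives 0.5/0.925 = 54.1% v 0.5/0.975 = 51.3%, or +2.8 points.

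**Scale.** One participant in 12 is 8.3 points. The standard error of the difference with 12 per arm is √(2 × 0.25/12) = 20 points.

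**Equal but prognostic stopping.** The comparison is unbiased, yet each arm's rate still moves: 55.6% against a true 50% in the first row. That matters if the rate feeds a sample-size calculation.

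**The case against.** **The bias is not demonstrated.** Bias in the comparison needs stopping that is both prognostic and unequal by arm. Active current is set below the tolerated maximum, participants are asked every ten minutes whether it should change, and distress ends the session rather than participation (Section 9.6.3). Section 4.2 reports no adverse events in the sponsor's earlier studies. Nothing in the documents links intolerance of the current to weaning prospects. This stands: the point is a risk, not an established bias.

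**The plausible size is small.** At the planned 10% drop-out, a shift of 3 to 5 points is less than one participant per arm and well inside sampling error, on a secondary endpoint of a pilot. This also stands, and it limits the weight of the point.

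**Many early stoppers would be excluded, not censored.** This is a fair reading of the per-protocol sentence. It does not rescue the plan, because the shift under exclusion is similar or slightly larger. It does mean that collecting the data is not enough: the analysis-set sentence must change too. For weaning success, analysed by Poisson regression, the problem is exclusion or missing data, not Kaplan-Meier censoring.

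**Leaving the trial is inferred.** Section 14.1 speaks of ending study treatment, and the daily ventilator-free record might be meant to continue. The text is ambiguous here. But Section 12.6 describes even a weaned patient as withdrawn from the study, and Appendix A ends at the early visit.

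**Charts could be consulted later.** Possibly, so a reader should not infer that the status is lost beyond recovery. The plan does not ask for it, and retrieval depends on what consent allows.

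**Conclusion.** The gap in data collection is clear from the text: no weaning status is scheduled after someone stops unweaned, and Section 17 offers hospital residence as reassurance without using it to collect the outcome. Under Section 17 these participants would be excluded or censored at stopping. Either may bias time to wean and weaning success if stopping is related to prognosis and unequal between arms.

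With no true effect, 50% weaning and only non-weaners stopping, the censored comparison shifts by about +5 points at 15% v 5% of each arm (about +3 if partly linked) and about +11 at 20% v 0%. It shifts by about zero if stopping is equal or unrelated. All these rates are assumptions, and the sign reverses if would-be weaners are the ones who stop.

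A reader might infer that the comparison *is* informatively censored, or that Section 17 denies any censoring concern. The documents support neither. They give no stopping data by arm, and Section 17 says only that no significant concern is anticipated. The point is worth acting on because the remedy is cheap and the weaning data are meant to size the next trial.

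**What to change.** 1. **Sections 12.6 and 14.1:** state that stopping stimulation is not leaving the trial. Take ventilator, weaning and vital status from the hospital chart to Day 45 for every randomised participant who has not withdrawn consent to data use. Add this to Appendix A.
2. **Section 17 and synopsis, analysis set:** amend the per-protocol sentence so that the weaning analyses include all randomised participants. Otherwise the newly collected outcomes could still be dropped.
3. **Section 17, censoring sentence:** replace it with a rule. Censor at Day 45, at withdrawal of consent to data, or at transfer with no obtainable status. Handle death by a separately stated rule.
4. **Reporting:** give the number censored before Day 45 by arm and reason. Add two sensitivity analyses, one counting those censored early as not weaned and one counting them as weaned, since the error can go either way.

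**Cost:** wording in a few places and chart review for the 2 to 3 participants expected to stop early. There is no extra visit, procedure or enrolment. Consent must cover continued chart review.
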